Project: MADCO-PC Study (Markers of Alzheimer's Disease and Cognitive Outcomes after Perioperative Care

Clinicaltrials.gov registration Number: NCT01993836

Date: July 15, 2016

Document: MADCO-PC Protocol Brief Summary 7-12-2016

MADCO-PC Protocol Summary

Purpose:

This study will examine the hypothesis that changes in the cognition (i.e. thinking and memory) after anesthesia and surgery are correlated with changes in markers of Alzheimers Disease in the fluid around the brain and spinal cord (i.e. cerebrospinal fluid, or CSF), and/or changes in brain connectivity. The investigators will also examine whether different types of anesthesia have different effects on these CSF markers of Alzheimers disease, or different effects on thinking and memory after anesthesia and surgery, or differential effects on the correlation between cognitive changes and CSF marker changes.

Outcome Measures:

Primary Outcome Measure: Assess the correlation between perioperative change in CSF Markers of Alzheimers Disease and perioperative cognitive change. [Time Frame: up to 6 weeks]

We will assess the magnitude of the Spearman correlation coefficient for the relationship between perioperative change in CSF Markers of Alzheimers Disease and the perioperative change in the continuous cognitive index score.

Secondary Outcome Measures:

1. Continuous cognitive index score change [Time Frame: 1 year]

We will examine the difference in the continuous cognitive index score over time in the subjects treated with propofol versus those treated with isoflurane, and versus such changes seen in non-surgical controls. We will also assess the correlation between perioperative change in CSF Markers of Alzheimers Disease and perioperative cognitive change in patients randomized to receive isoflurane vs propofol.

2. Assess CSF Markers of Alzheimers Disease [Time Frame: up to 6 weeks]

We will examine CSF Markers of Alzheimer's Disease over time in the subjects treated with propofol versus those treated with isoflurane, and versus any such changes seen in non-surgical controls.

3. Acute Perioperative CSF Tau/Abeta ratio change [Time Frame: 24 hours]

We will measure the perioperative change in the CSF tau/Abeta ratio from the start of anesthesia/surgery to 24 hours later, and compare this to changes seen in the non-surgical controls at the cognate time points.

4. Chronic Perioperative CSF Tau/Abeta ratio change [Time Frame: 1 year]

We will measure the stability of any acute 24 hour postoperative changes in the CSF tau/Abeta ratio out to 6 weeks and 1 year later in surgical patients, and compare these changes to any changes seen over time in the non-surgical controls.

Enrollment Numbers, Inclusion and exclusion criteria

Targeted enrollment is 108 surgical patients who complete the 6 week follow up visit, which provides >80% power to detect a spearman correlation coefficient of 0.3 or greater (a low-

moderate correlation) for the aforementioned primary outcome measure. 54 non-surgical controls will also be enrolled as described below.

Ages Eligible for Study: 60 Years and older

Genders Eligible for Study: Both

Inclusion Criteria:

- Age 60 year or older
- Surgery scheduled to last at least 2 hours (including time for anesthesia induction, etc)
- English speaking ability.

Exclusion Criteria:

- Inmate of a correctional facility (i.e. prisoners).
- Pregnancy
- Documented or suspected family or personal history of malignant hyperthermia.
- Patient unable to receive either propofol or isoflurane due to allergy or other specific contraindication.

Inclusion criteria for the non-surgical controls are the same as those described above, with the exception of the second inclusion criteria (surgery scheduled to last at least 2 hours). Non-surgical controls (i.e. community dwelling older adults) will be recruited from several Duke research subject registries, and will be matched to surgical patients on a 2:1 basis (2 surgical patients for each non-surgical control) based on age, sex, and educational status. Non-surgical controls will undergo the same study procedures as surgical patients at the same cognate time intervals.

Study Procedures:

Cognition: Our full POCD cognitive test battery (as described in Newman MF et al, NEJM, 2001) is performed on study patients within one month (typically one week) prior to anesthesia and surgery, and then again six weeks and one year after anesthesia and surgery.

All patients are screened for delirium on postoperative days one through seven by our experienced neurocognitive testing team.

Biochemical Studies/Samples: CSF and peripheral blood samples are obtained immediately prior to anesthesia and surgery, 24 hours later, six weeks later, and one year later. These samples will be assayed for Alzheimer's disease biomarkers (including amyloid beta, tau and phospho-tau) as well as inflammatory markers and other biomarkers of interest.

Brain imaging: Functional MRI scans are performed within one month prior to Anesthesia and surgery, and then again six weeks after anesthesia and surgery. Multiple scan sequences are used to evaluate anatomic and functional Brain connectivity.

For more information, please see:

<https://clinicaltrials.gov/ct2/show/NCT01993836?term=[name]&rank=1>

Newman MF et al, *NEJM*, 2001.

[name] M et al, *Anesthesiology Clinics*, 2015.

[name] M et al, *JCTVA*, 2014.

Project: MADCO-PC Study (Markers of Alzheimer's Disease and Cognitive Outcomes after Perioperative Care

Clinicaltrials.gov registration Number: NCT01993836

Date: September 5, 2017

Document: SAP_2405_Berger_v5

Statistical Analysis Plan

ACTIVATE: CSF trajectories

SAP Version: 5.0

SAP Date: 9/5/17

Author: [name]

Primary Investigator: [name]

Revisions/Notes:

V2.0 5/20/17: Revised SAP structure to highlight hypotheses of interest, added data flow diagram and table shell

V3.0 6/5/17: Made primary and secondary hypotheses to match order in ct.gov listing. Added in current table 1

V4.0 7/28/17: There are 2 patients whose CSF data has yet to be analyzed, currently analyzed with imputation but if results returned from the lab will want to incorporate that data into the analysis.

Study Objective: AD biomarker change in CSF and relationship with cognitive change.

Animal studies have shown that inhaled anesthetic agents increase the levels of Alzheimer's disease related neural markers (such as amyloid beta and tau). Several studies have measured blood serum markers indirectly related to Alzheimer's disease in patients randomized to inhaled versus intravenous anesthesia, no randomized controlled trial has ever examined these markers in the cerebrospinal fluid of patients given inhaled versus intravenous anesthesia. No randomized controlled study to date has ever examined whether inhaled anesthetics (versus intravenous anesthetics) alter brain levels of Alzheimer's associated markers in humans, and/or whether such changes (if they occur) correlate with POCD or other cognitive changes, or changes in brain structure or activity after surgery and anesthesia.

Here, we propose to measure Alzheimer's disease-related neural markers in the cerebrospinal fluid (CSF) of patients exposed to anesthesia during surgery, as well as in non-surgical controls (age matched community dwelling individuals age 60 and over). These studies should clarify the effect of common anesthetic agents on Alzheimer's disease related neural markers and cognitive outcomes.

1. Hypotheses:

- i. The degree of increase in AD marker CSF levels will be associated with cognitive outcomes.
- ii. AD biomarkers will increase from baseline to the 24 hours postop time point.

2. Outcomes:

Outcome	Description	Specifications	Variables and Source
Cognitive Change from baseline to 6 weeks	As a numeric variable (continuous cognitive change) or as binary outcome (POCD w/>>1 or 2 SD drop)	Derive factor weights within sample and compare to that of historical non-cardiac population	Use bluecap database for cognitive data

3. Study population and datasets:

Inclusion Criteria: Patients undergoing urologic, general or other surgical procedures, aged 60 and above, English speaking **[Per PI will include all patients with BL and 6 week cognitive data available and run imputations to fill in missing CSF data in primary analysis]**

Exclusion Criteria: inmate of a correctional facility (i.e. prisoners), documented or suspected family or personal history of malignant hyperthermia, unable to receive either propofol and/or isoflurane due to allergy or other specific contraindication, receiving systemic chemotherapy after the first cognitive testing session and before the 6 wk or 1 year follow up cognitive testing sessions, major head trauma that occurs after the first cognitive testing session and before the 6 wk or 1 year follow up cognitive testing sessions.

Data Set Sources

Penn AD CSF data— Contains baseline, 24hr, and 6 week AD biomarker analysis (tau, abeta, p-tau)
Patient characteristics data—IT pull ticket 2494

Cognitive Data--Use BlueCap database and data entry from CRC groupAD Biomarkers (Primary Variable of Interest)

Variable names	Description	Specifications (e.g. formula)
CSF A beta	Measured BL, 24 hr, 6 weeks	Look at individual time points, trajectory, and change BL to 24 hr, and BL to 6 weeks
CSF tau		
CSF phospho-tau		
CSF tau/a beta		
CSF p-tau/a beta	Quotient of p-tau and a-beta at each time point	

4. Adjustment Variables

Candidate Covariates	Description
Anesthetic Type (randomized)	Propofol vs. Isoflurane group
Demographics	age, BMI, race, sex, years of education
Baseline Cognitive Status	MMSE score (raw and categorical [≥ 25 , 20-24, < 20]), mean cognitive index, domain scores
Clinical Factors	ASA status, surgical type (urology, orthopedics, plastics, thoracic surgery, general/abdominal, gynecologic etc), open incision vs laparoscopic approach, epidural block, regional block, vs no block, surgery duration (from incision to end surgery time stamps), IO BIS (mean of median filtered), ET aaMAC (mean of medians filtered), propofol dose, ketamine use, dexmedetomidine use, admitted to ICU by POD1

6. Statistical Methods and results

 - b. Association of CSF change with binary cognitive outcome via t-tests or Wilcoxon rank sum tests.
 - i. Summary statistics on ACTIVATE _ResultsSummary_0727 sheet CSFchange
 - ii. Still need to determine how to run non-parametric test on MI datasets (as of 7/28)
 - c. Added 7/27/17: Association of baseline CSF with numeric baseline cognition and cognitive change via spearman correlation
- 3. Multivariate Analysis
 - a. Use linear and logistic regression to study association of CSF with cognition adjusting for patient characteristics
 - b. Candidate variables for model: age, ASA status, years of education, baseline cognitive index, baseline MMSE score, baseline CSF AD biomarker measures, CSF AD biomarker changes from before to after surgery (from before to 24 hrs postop, and from before to 6 weeks postop), DARS, mean of median end tidal MAC fraction (age adjusted), surgery type, surgery length, MAC-hours, cumulative propofol dosage
 - c. Adjustment variables added as indicated via univariate association with outcome and as allowed by sample size restrictions in model

- d. Model assumptions will be evaluated and performance measured
 - i. Numeric cognitive change: assess residual Q-Q plot, mse, R2
 - ii. Binary cognitive change: C-index, R2, GOF
- 4. Investigate CSF associations with individual cognitive domains in exploratory analysis (figure 3). This would help evaluate for the possibility that pre to post op changes in CSF AD biomarkers may be particularly related to changes in one particular cognitive domain (such as memory) rather than global cognition.

Hypothesis 2: AD biomarkers will increase from baseline to the 24 hours postop time point.

- 1. Data visualization of CSF change over time (BL, 24hrs, 6wk)—Figure 1
- 2. Calculate change from baseline to
 - a. 24 hrs—assess if change is significant via t-test or Wilcoxon Signed Rank Test
 - b. 6 week—assess if change is significant via t-test or Wilcoxon Signed Rank Test
- 3. CSF trajectory analysis (BL, 24hr, 6 week)—repeated measures mixed model

7. Proposed Tables and Figures

- 1. Table 1 describing baseline characteristics of the study cohort
 - a. Demographics: age, BMI, race, sex, years of education
 - b. Baseline Cognitive status: MMSE score (raw and categorical [≥ 25 , 20-24, < 20]), mean cognitive index, domain scores
 - c. Baseline CSF measures
 - d. Clinical factors: ASA status, surgical type (urology, orthopedics, plastics, thoracic surgery, general/abdominal, gynecologic etc), open incision vs laparoscopic approach, epidural block, regional block, vs no block, surgery duration (from incision to end surgery time stamps), IO BIS (mean of median filtered), ET MAC (mean of medians filtered), propofol dose, ketamine use, dexmedetomidine use, admitted to ICU by POD1
- 2. Figure 1
 - a. CSF A beta as a function of time- preop, 24 hr postop, 6 weeks postop
 - b. CSF tau as a function of time- preop, 24 hr postop, 6 weeks postop
 - c. CSF phospho-tau as a function of time- preop, 24 hr postop, 6 weeks postop
 - d. CSF tau/a beta ratio as a function of time- preop, 24 hr postop, 6 weeks postop
 - e. CSF p-tau/a beta ratio as a function of time- preop, 24 hr postop, 6 weeks postop
 - f. (Could also consider making stratified plots for 2A-2D with two lines for each graph, one line for patients with POCD by either a 1 or 2 SD drop in any cognitive domain rule, and one line for patients without POCD)
- 3. Figure 2
 - a. Dot plot- CSF tau change from preop to 24 hrs on Y axis, Continuous Cognitive index change from before to 6 weeks on X axis, each patient is one dot on the graph
 - b. Dot plot- CSF tau change from preop to 6 weeks on Y axis, Continuous Cognitive index change from before to 6 weeks on X axis, each patient is one dot on the graph;

- c. (or could combine plots 3A and 3B by just plotting maximal increase in CSF tau from preop to either 24 hrs or 6 weeks on Y axis- whichever is larger- and cognitive change index from preop to 6 weeks postop on X axis)
- d. C, D- equivalent of 2a,2b, but with amyloid beta instead of tau
- e. E, F- equivalent of 2a,2b, but with p-tau instead of tau
- f. G Dot plot- CSF tau/abeta ratio change from preop to 24 hrs on Y axis, Continuous Cognitive index change from before to 6 weeks on X axis, each patient is one dot on the graph;
- g. H Dot plot- CSF/Abeta tau ratio change from preop to 6 hrs on Y axis, Continuous Cognitive index change from before to 6 weeks on X axis, each patient is one dot on the graph;

4. Repeating Figure 2 A-D with the X axis representing change in each of the 4 individual cognitive domain scores rather than the overall cognitive index score.

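### The correlation of baseline CSF with baseline cognition (SAP 6, Hypothesis 1, item 2c) is specified only in crude form; an age-adjusted coefficient should be reported beside it

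*SAP*

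**What the plan says.** SAP section 6, Hypothesis 1, separates univariate analysis (item 2) from multivariate analysis (item 3). Item 2c, in the univariate group, reads: "Added 7/27/17: Association of baseline CSF with numeric baseline cognition and cognitive change via spearman correlation". It therefore holds two analyses: baseline CSF against baseline cognition, and baseline CSF against cognitive change. Neither has a covariate.

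Item 3a opens the adjusted analysis in general terms: "Use linear and logistic regression to study association of CSF with cognition adjusting for patient characteristics". The candidate variables in 3b begin with "age, ASA status, years of education, baseline cognitive index, baseline MMSE score, baseline CSF AD biomarker measures". Item 3c decides which of them enter: "Adjustment variables added as indicated via univariate association with outcome and as allowed by sample size restrictions in model". Item 3d describes how the models will be assessed and names two outcomes: "Numeric cognitive change: assess residual Q-Q plot, mse, R2" and "Binary cognitive change: C-index, R2, GOF". The only entry in the outcomes table (SAP section 2) is "Cognitive Change from baseline to 6 weeks".

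The protocol's eligibility section sets a minimum age of 60 with no maximum, and targets 108 surgical patients who complete the 6-week visit.

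**The concern.** The baseline-cognition half of 2c compares levels between people at one time point. In a sample running from 60 upwards, age may be related both to the CSF markers and to cognitive scores. The crude Spearman then carries whatever part of the association comes from age alone, and a reader cannot tell that part from a link between marker and cognition among people of the same age.

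For most associations in the plan this would not matter, because an adjusted model follows the crude analysis. Here none is specified. If the baseline coefficient is reported and interpreted, it will have no adjusted counterpart. What is at stake is how one exploratory coefficient per marker or ratio (five are listed in SAP section 3) is interpreted.

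**Working it through.** **1. Is there an adjusted counterpart?** Each later analysis, by outcome:

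| Place in SAP | Outcome | Role of baseline cognition |
|---|---|---|
| Section 2, outcomes table | Cognitive change to 6 weeks | Not an outcome |
| Section 6, H1, 3b | (candidate list) | Candidate predictor |
| Section 6, H1, 3d | Numeric and binary cognitive change | Not an outcome |
| Section 6, H1, 4 | Individual domains, motivated by change in them | Not named |
| Section 6, Hypothesis 2 | CSF over time | None |

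No adjusted analysis is specified for baseline cognition. The cognitive-change half of 2c does have one: baseline CSF, age and years of education are all candidates in 3b.

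**2. The plan's own figure.** The documents give no power or effect size for 2c. The nearest figure is the protocol's power above 80% for a Spearman coefficient of 0.3 with 108 patients. Using Fisher's z with Spearman variance 1.06/(n-3), and assuming two-sided 0.05 (alpha and sidedness are not stated):

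- SE = sqrt(1.06/105) = 0.1005
- atanh(0.3)/SE = 0.3095/0.1005 = 3.08
- power = Phi(3.08 - 1.96) = 86.9%

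This agrees with the protocol, and the present point does not affect it.

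**3. Size of the age effect.** Inputs: n = 108 (protocol) and the correlations of age with marker and with cognition (assumed; the documents give neither). If age is the only link, the induced correlation is r = r(age, marker) x r(age, cognition). The chance of p<0.05 is Phi(d - 1.96) + Phi(-d - 1.96), where d = atanh(|r|)/0.1005.

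| Age-marker | Age-cognition | Induced r | d | Chance of p<0.05 |
|---|---|---|---|---|
| 0.2 | -0.2 | -0.04 | 0.40 | 6.8% |
| 0.3 | -0.4 | -0.12 | 1.20 | 22.4% |
| 0.4 | -0.5 | -0.20 | 2.02 | 52.3% |

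The product is on the Pearson scale. Converting it to the Spearman scale with (6/pi) x arcsin(r/2) lowers the three results to 6.7%, 20.9% and 48.7%.

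**4. Simulation check.** Bivariate-normal data, n = 108, 20,000 runs per setting, with marker and cognition depending only on age. The signs are as above.

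| Age correlations (absolute) | Crude Spearman, p<0.05 | Age-partial Spearman, p<0.05 |
|---|---|---|
| 0.2, 0.2 | 7.0% | 4.9% |
| 0.3, 0.4 | 21.9% | 5.0% |
| 0.4, 0.4 | 35.4% | 5.0% |

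**5. Cost of adjustment.** With k covariates the variance becomes 1.06/(n-3-k). Power for a coefficient of 0.3 is 86.9% with none, 86.6% with one (age) and 85.9% with three (age, education, sex).

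**The case against.** The strongest defence is that 2c is labelled as univariate and does what its label says. It was added late, neither SAP hypothesis concerns it, it is not among the protocol's primary or secondary outcomes, and no proposed figure shows it. The SAP draws no causal conclusion from it. This stands, and it is why the point is minor.

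A second defence is that 3a speaks of cognition without qualification, so an adjusted baseline model could fall under it. Item 3d is also a list of diagnostics, not a definition of outcomes. But 3b offers the baseline cognitive index as a predictor, and every outcome named elsewhere is change. The fair statement is that an adjusted baseline analysis is not specified, not that it is ruled out.

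Third, the percentages are not type I errors of the Spearman test. If age links the two variables, their marginal correlation truly is non-zero and the test detects it correctly. This also stands: the difficulty is interpretation. The percentages also depend on assumed correlations, and one positive age-marker range need not suit A beta or the ratios.

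A reader might infer more than the documents support:

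- **Control matching as evidence.** The protocol matches controls "based on age, sex, and educational status" but gives no reason. Matching makes groups comparable and says nothing about confounding of a correlation within patients.
- **The cognitive-change half.** Item 3 already offers adjustment for it. Under 3c, age is not guaranteed to enter, but that is a separate matter.
- **Education as a confounder.** It would have to relate to the CSF markers as well as to test scores, and the documents do not show that. The argument rests on age.
- **Effect on the CSF-change result.** Nothing in the SAP makes 2c the context for interpreting that result.

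**Conclusion.** The gap is real but small. For baseline CSF against baseline cognition, the SAP specifies a crude Spearman and no adjusted analysis. Under the assumed age correlations, shared ageing alone gives p<0.05 in about 7% to 52% of samples of 108, per marker. The bottom of that range is hardly distinguishable from 5%, and the top needs both assumed correlations at their upper limits. The calculation also assumes that age is the only link, that 108 patients contribute, and that the test is two-sided at 0.05. The size is therefore unknown until the data show how age relates to each marker and to cognition. The primary outcome, its power statement and the cognitive-change analyses are unaffected.

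**What to change.** In item 2c, for the baseline-cognition half only, add a partial Spearman correlation controlling for age. Report it beside the crude coefficient for each marker and ratio, state that interpretation rests on the adjusted value, and label the crude value descriptive. Years of education and sex may be added for precision or consistency with the covariates in SAP section 4, but the case for the change does not depend on them. Leave the cognitive-change half as it is.

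The cost is a sentence in the SAP and a few lines of code. Age, sex and education are already planned for Table 1 and used in the imputation model, so no new data are needed. The loss of power is about 0.3 percentage points with age alone and about one point with all three covariates.

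### The adjusted CSF-cognition models admit covariates only by their univariate link to the outcome, so weak or masking confounders, notably the same marker's baseline value, can be dropped

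*SAP*

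**What the plan says.** SAP section 6, Hypothesis 1, item 3a sets out the adjusted analysis: "Use linear and logistic regression to study association of CSF with cognition adjusting for patient characteristics". Item 3b gives the candidates, beginning "Candidate variables for model: age, ASA status, years of education, baseline cognitive index, baseline MMSE score, baseline CSF AD biomarker measures" and ending "DARS, mean of median end tidal MAC fraction (age adjusted), surgery type, surgery length, MAC-hours, cumulative propofol dosage". Item 3c gives the entry rule: "Adjustment variables added as indicated via univariate association with outcome and as allowed by sample size restrictions in model". It states no p-value or effect threshold, no numerical cap and no covariate that is always in the model. Nothing elsewhere in the protocol or SAP fixes the adjustment set.

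SAP section 4 has a second candidate list, and the two differ. The randomised arm ("Anesthetic Type (randomized") is only in section 4. So are BMI, race and sex, from the line "age, BMI, race, sex, years of education". Baseline CSF, DARS and MAC-hours are candidates only in 3b.

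Item 2c, added in July 2017, plans a separate look at "Association of baseline CSF with numeric baseline cognition and cognitive change via spearman correlation". The SAP therefore treats baseline CSF as possibly related to the outcome, yet 3b and 3c leave it optional in the models of CSF change. Item 2b already points to results: "Summary statistics on ACTIVATE _ResultsSummary_0727 sheet CSFchange".

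**The concern.** A confounder distorts the CSF coefficient through two links, one to CSF change and one to cognition. The rule in 3c examines only the second, and only marginally. Two kinds of covariate can be lost:

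- **Weak confounders.** Their link with cognition is too small to be detected reliably at this sample size, although their link with CSF change may be clear.
- **Masking confounders.** Their effect on cognition is partly cancelled by the CSF effect, so they look unimportant taken alone.

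The same marker's baseline value is a natural candidate for the second kind. Regression to the mean ties it negatively to the marker's change. If high baseline tau and rising tau both predict decline (the first is an assumption; the second is close to the SAP's Hypothesis 1), each hides part of the other. The screen could then discard the covariate that would reveal the hypothesised effect.

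These are the plan's only covariate-adjusted models of CSF against cognition, so they will be read as the check on whether the primary correlation survives adjustment.

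**Working it through.** **Inputs from the documents.** n=108 surgical patients completing the 6-week visit, and a Spearman correlation of 0.3 with more than 80% power (protocol, enrollment section). The documents give no alpha, screening threshold, covariate correlations or POCD rate. Assumed: two-sided alpha 0.05 and screens at p<0.05, 0.10 and 0.20.

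**1. The plan's own figure.** Fisher z power is Φ(atanh(r)·√((n−3)/v) − 1.96). With r=0.3 and n=108, atanh(0.3)·√105 = 0.3095 × 10.247 = 3.172.
- v=1: Φ(1.212) = 88.7%.
- v=1.06 (Spearman): Φ(3.081 − 1.960) = 86.9%.

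The claim of more than 80% is reproduced.

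**2. Chance that a covariate fails the screen.** With λ = atanh(r)·√105 and critical value z, P(omitted) = Φ(z − λ) − Φ(−z − λ). Example: r=0.2 gives λ=2.077, so at p<0.05 P = Φ(−0.117) = 45%.

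| True r with numeric outcome | p<0.05 | p<0.10 | p<0.20 |
|---|---|---|---|
| 0.10 | 82% | 73% | 59% |
| 0.15 | 66% | 54% | 39% |
| 0.20 | 45% | 33% | 21% |
| 0.25 | 26% | 17% | 9% |
| 0.30 | 11% | 6% | 3% |

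**3. False positives with no CSF effect.** Simulation: independent normal confounders, each correlated 0.3 with CSF change, plus six noise candidates; at most 8 terms including CSF; smallest p enters first; 10,000-20,000 replicates.

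| Setting | p<0.05 | p<0.10 | p<0.20 | All forced in |
|---|---|---|---|---|
| Three confounders, r=0.1 with outcome | 7.5% | 5.8% | 4.7% | 4.9% |
| Three, r=0.2 | 8.8% | 6.4% | 5.2% | 4.9% |
| Three, r=0.3 | 6.6% | 5.5% | 5.1% | 5.1% |
| One, r=0.2 | 5.3% | 5.1% | 4.8% | 5.0% |

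**4. One masking confounder.** Assumed true standardised CSF coefficient 0.30, confounder coefficient −0.20, correlation 0.3 between confounder and CSF change.
- Marginal correlation of the confounder with the outcome: −0.20 + 0.30 × 0.3 = −0.11.
- Then λ = atanh(0.11)·√105 = 1.132, and the formula in step 2 gives omission of about 80%, 69% and 55% at the three thresholds (simulation: 79%, 69%, 54%).
- CSF coefficient if the confounder is never adjusted for: 0.30 + (−0.20) × 0.3 = 0.24.
- Under 3c (simulated): about 0.25-0.27 on average, with power 76-80% from strictest to most lenient screen.
- With the confounder in a four-variable core and the rest screened at p<0.20: power about 84% (83-85% across runs).

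**5. Why baseline CSF is a plausible case.** With equal SDs and stability ρ between visits, corr(baseline, change) = −√((1−ρ)/2). At an assumed ρ of 0.82 this is −√0.09 = −0.30; at 0.90 it is −0.22 and at 0.95 it is −0.16. A negative link with change, together with a baseline effect on cognition in the same direction as the CSF-change effect, is the mirror image of step 4.

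**The case against.** The strongest reply has four parts.

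- **The false-positive harm is conditional.** It needs several same-direction confounders and a strict screen, and the SAP states no strict screen. This stands. At p<0.20 the error under 3c is nominal, and for r=0.2 a forced core does no better on this measure: 5.4/5.1/5.0/4.9% with 0/1/2/3 of the confounders in the core, against 5.2%. The argument for the core rests on masking, where it gains about four points of power even at p<0.20.
- **Only baseline CSF has a reason behind its assumed link with CSF change.** This stands too. Age, education and baseline cognition belong in the core on subject-matter grounds, not because of a calculation here.
- **The list mismatch is partly benign.** Section 4 can be read as a general list and 3b as specific to these models; CSF markers have their own table in section 3; and the MAC and propofol variables partly carry the arm. Fair, but the SAP does not say which list governs.
- **If confounding were strong, the unadjusted analysis would suffer more.** True: under the three-confounder assumptions at r=0.2, an unadjusted linear test rejects 46% of the time, and 3c removes most of that.

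A reader might also infer that covariates were chosen in the light of results, because July 2017 summaries are cited. The documents show only that results existed while the rule was still open, not that they were used in this way.

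**Conclusion.** The point holds in a limited form. Item 3c applies an outcome-only screen with no forced covariates, and that can drop weak confounders (true r of about 0.1-0.2) and masking ones. The plausible cost is an attenuated CSF coefficient (0.25-0.27 for a true 0.30) and 4 to 8 points of power (76-80% against about 84%) under one assumed masking pattern. False-positive inflation reaches about 9% only in the least favourable setting tried.

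Two stronger readings are not supported. Moderate confounders are not routinely lost: at r=0.3 with the numeric outcome, omission is 3-11%. The primary result is not put in doubt by this rule: the protocol's primary measure is an unadjusted Spearman correlation, which 3c does not touch.

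All correlations, thresholds and the stability figure are assumptions. The simulations use independent normal covariates.

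**What to change.** Reword item 3c along these lines:

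- Age, years of education, baseline cognitive index and the baseline value of the same CSF marker are always included, in both the linear and logistic models, whatever their univariate p-value.
- Further candidates come from one list that merges section 4 and item 3b. They may be added by a stated lenient screen (for example p<0.20) up to a stated cap. The cap is counted in model degrees of freedom, because surgery type has at least six named levels; sparse levels are collapsed.
- The text says how screening p-values are obtained across the imputed datasets.
- The text says that the core set was fixed after the July 2017 summaries existed.

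Keeping a screen for the remaining candidates still gives confounders outside the core a chance to enter.

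**Cost.** SAP wording only, using variables already listed. In the linear model, four extra degrees of freedom change Fisher z power at a partial correlation of 0.3 from 88.7% to Φ(0.3095·√101 − 1.96) = 87.5%. In simulation without confounding, the new rule gave 86.7-87.6% against 87.0-87.1% under 3c. The logistic model is the tighter case. CSF plus the core is 5 terms on 22-43 events at assumed POCD rates of 20-40%, or about 4 to 9 events per term. Simulated Wald type I error there was 4.6-5.6%, but the model becomes heavy if events are fewer.
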